4.4.2 LESS EFFECTIVE METHODS OF CONTRACEPTION

- Diaphragm with spermicide
- Cervical cap with spermicide
- Vaginal sponge
- Male Condom without spermicide
- Progestin only pills by WOCBP subject or male subject's WOCBP partner
- Female Condom. A male and female condom must not be used together.

WOCBP must not be pregnant or breastfeeding while they are receiving study treatment and up to 5 months from the last dose of Nivolumab. MOCBP must not impregnate a female while they are receiving the study treatment and up to 7 months after the last dose of Nivolumab.

4.5 SUBJECT WITHDRAWAL/DISCONTINUATION CRITERIA

Subjects may withdraw consent at any time for any reason or be dropped from the trial at the discretion of the investigator. In addition, a subject may be withdrawn by the investigator if enrollment into the trial is inappropriate, the trial plan is violated, or for administrative and/or other safety reasons.

The End of Treatment and Follow-up visit procedures are listed in Section 6 (Protocol Flow Chart) and Section 7.9 (Visit Requirements). After the end of treatment, each subject will be followed for 30 days for adverse event monitoring (serious adverse events will be collected for 100 days after the end of treatment). Subjects who discontinue for reasons other than progressive disease will have post-treatment follow-up for disease status until disease progression, initiating a non-study cancer treatment, withdrawing consent or becoming lost to follow-up or the end of the study whichever occurs first. After documented disease progression each subject will be followed by telephone for overall survival until death, withdrawal of consent, or the end of the study, whichever occurs first.

4.6 SUBJECT REPLACEMENT STRATEGY

Subjects will not be replaced. The power calculation allows for early study withdraw.

5.0 STUDY DRUG

5.1 INVESTIGATIONAL PRODUCT

The investigator shall take responsibility for and shall take all steps to maintain appropriate records and ensure appropriate supply, storage, handling, distribution and usage of investigational product in accordance with the protocol and any applicable laws and regulations.

Clinical Supplies will be provided by BMS for all sites. Nivolumab will be available as an injection at 100 mg/10 ml (10 mg/ml) and will be given at a flat dose of 480 mg.

5.2 PACKAGING AND LABELING INFORMATION

Clinical supplies will be affixed with a clinical label in accordance with regulatory requirements.

5.3 CLINICAL SUPPLIES DISCLOSURE

This trial is open-label; therefore, the subject, the trial site personnel, the Sponsor Investigator and/or designee are not blinded to treatment. Drug identity (name, strength) is included in the label text; random code/disclosure envelopes or lists are not provided.

5.4 STORAGE AND HANDLING REQUIREMENTS

Clinical supplies must be stored in a secure, limited-access location under the storage conditions specified on the label.

An authorized person at the trial site must record receipt and dispensing of trial medication.

Clinical supplies may not be used for any purpose other than that stated in the protocol.

5.5 RETURNS AND RECONCILIATION

The investigator is responsible for keeping accurate records of the clinical supplies received from BMS or designee, the amount dispensed to and returned by the subjects and the amount remaining at the conclusion of the trial. The sponsor will provide BMS with a copy of the drug destruction certificate at the end of the study.

5.6 TREATMENT OUTLINE

The treatment to be used in this trial is outlined below in Table 2

Table 2. Trial Treatment

Drug	Dose/ Potency	Dose Frequency	Route of Administration	Regimen/ Treatment Period	Use
Nivolumab	480 mg	Q4W	IV infusion	Day 1 of each 4 week cycle starting 4-11 weeks after surgery for 6 doses	Experimental

Treatment will be administered on an outpatient basis. Protocol treatment (pre-surgical Nivolumab dose) must begin only after eligibility criteria are confirmed by the UC PI (registration), see study flow for more specific timeframes.

5.6.1 NIVOLUMAB INJECTION GUIDELINES

Nivolumab injection is to be administered as an IV infusion through a 0.2-micron to 0.22-micron pore size, low-protein binding (polyethersulfone membrane) in-line filter at the protocol specified doses and infusion times. It is not to be administered as an IV push or bolus injection. Nivolumab injection can be infused undiluted (10 mg/mL) or diluted with 0.9% Sodium Chloride Injection, USP or 5% Dextrose Injection, USP to protein concentrations as low as 0.35 mg/mL. During drug product preparation and handling, vigorous mixing or shaking is to be avoided. Instructions for dilution and infusion of Nivolumab injection may be provided in the clinical protocol or latest IB. Care must be

taken to assure sterility of the prepared solution, as the product does not contain any antimicrobial preservative or bacteriostatic agent. Nivolumab infusions are compatible with polyvinyl chloride (PVC) or polyolefin containers and infusion sets, and glass bottles. The latest IB contains specific instructions for the preparation of the Nivolumab infusion fluid and administration of infusion solution. Specific questions regarding preparation and administration may be referred to the sponsor for expertise on the topic.

5.6.2 COMPLIANCE CRITERIA

5.6.3 TIMING OF DOSE ADMINISTRATION

Trial treatment should be administered on Day 1 of each cycle after all procedures/assessments have been completed as detailed on the Trial Flow Chart (Section 6.0). Study Drug may be administered up to 3 days before or after the scheduled Day 1 of each cycle due to administrative reasons.

All trial treatments will be administered on an outpatient basis.

5.6.4 CONCOMITANT MEDICATIONS/VACCINATIONS (ALLOWED & PROHIBITED)

Medications or vaccinations specifically prohibited in the exclusion criteria are not allowed during the ongoing trial. If there is a clinical indication for one of these or other medications or vaccinations specifically prohibited during the trial, discontinuation from trial therapy or vaccination may be required. The investigator should discuss any questions regarding this with the Investigator/PI. The final decision on any supportive therapy or vaccination rests with the investigator and/or the subject's primary physician.

5.6.4.1 ACCEPTABLE CONCOMITANT MEDICATIONS

All treatments that the investigator considers necessary for a subject's welfare may be administered at the discretion of the investigator in keeping with the community standards of medical care. All concomitant medication will be recorded on the case report form (CRF) including all prescription, over-the-counter (OTC), herbal supplements, and IV medications and fluids. If changes occur during the trial period, documentation of drug dosage, frequency, route, and date may also be included on the CRF.

All concomitant medications received within 28 days before the first dose of trial treatment and 30 days after the last dose of trial treatment should be recorded. Concomitant medications administered after 30 days after the last dose of trial treatment should be recorded for SAEs and non-serious adverse events as defined in Section 8.

5.6.4.2 PROHIBITED CONCOMITANT MEDICATIONS

Subjects are prohibited from receiving the following therapies during the Screening and Treatment Phase of this trial:

- Biological therapy
- Immunotherapy not specified in this protocol
- Chemotherapy
- Investigational agents other than Nivolumab

- Live vaccines within 30 days prior to the first dose of trial treatment and while participating in the trial. Examples of live vaccines include, but are not limited to, the following: measles, mumps, rubella, varicella/zoster, yellow fever, rabies, BCG, and typhoid vaccine.
- Systemic glucocorticoids should be avoided if possible. Steroids are allowed as short bursts of 5-7 days if required for clinical indication (i.e. COPD) or to modulate symptoms from an event of clinical interest of suspected immunologic etiology. The chronic use of physiologic doses of corticosteroids may be approved after consultation with the Sponsor.

Subjects, who, in the assessment by the investigator, require the use of any of the aforementioned treatments for clinical management other than specified as allowed, should be removed from the trial. Subjects may receive other medications that the investigator deems to be medically necessary.

There are no prohibited therapies during the Post-Treatment Follow-up Phase.

5.6.5 NIVOLUMAB DOSE MODIFICATION

Adverse events (both non-serious and serious) associated with Nivolumab exposure may represent an immunologic etiology. These adverse events may occur shortly after the first dose or several months after the last dose of treatment. Nivolumab must be withheld for drug-related toxicities and severe or life-threatening AEs as per Appendix 2 below.

Nivolumab administration should be delayed for the following:

- Any Grade ≥ 2 non-skin, drug-related adverse event, with the following exceptions:
 - Grade 2 drug-related fatigue or laboratory abnormalities do not require a treatment delay
- Any Grade 3 skin, drug-related adverse event
- Any Grade 3 drug-related laboratory abnormality, with the following exceptions:
 - Grade 3 amylase or lipase abnormalities that are not associated with symptoms or clinical manifestations of pancreatitis do not require a dose delay.
 - If a subject has a baseline AST, ALT, or total bilirubin that is within normal limits, delay dosing for drug-related Grade ≥ 2 toxicity
 - If a subject has baseline AST, ALT, or total bilirubin within the Grade 1 toxicity range, delay dosing for drug-related Grade ≥ 3 toxicity
- Any adverse event, laboratory abnormality, or intercurrent illness, which, in the judgment of the investigator, warrants delaying the dose of study medication

5.6.5.1 MANAGEMENT ALGORITHMS FOR IMMUNO-ONCOLOGY AGENTS

Immuno-Oncology (I-O) agents are associated with adverse events that can differ in severity and duration than adverse events caused by other therapeutic classes. Nivolumab is considered an immuno-oncology agent in this protocol. Early recognition and management of adverse events associated with immuno-oncology agents may mitigate severe toxicity. Management algorithms have been developed to assist investigators in assessing and managing the following groups of adverse events:

- Gastrointestinal
- Renal

- Pulmonary
- Hepatic
- Endocrinopathies
- Skin
- Neurological.

The algorithms recommended for utilization in this protocol are found in the Investigator Brochure and are included in Appendix 2 of this protocol.

For subjects expected to require more than 4 weeks of corticosteroids or other immunosuppressants to manage an adverse event, consider recommendations provided in Appendix 2.

Because of the potential for clinically meaningful Nivolumab related AEs requiring early recognition and prompt intervention, management algorithms have been developed for suspected pulmonary toxicity, GI, hepatotoxicity, endocrinopathy, skin toxicity, neurological toxicity and nephrotoxicity.

5.6.5.2 DOSE MODIFICATIONS FOR NIVOLUMAB

Dose reductions or dose escalations are not permitted.

5.6.5.3 CRITERIA TO RESUME NIVOLUMAB

Subjects may resume treatment with study drug when the drug-related AE(s) resolve to Grade ≤ 1 or baseline value, with the following exceptions:

- Subjects may resume treatment in the presence of Grade 2 fatigue.
- Subjects who have not experienced a Grade 3 drug-related skin AE may resume treatment in the presence of Grade 2 skin toxicity.
- Subjects with baseline Grade 1 AST/ALT or total bilirubin who require dose delays for reasons other than a 2-grade shift in AST/ALT or total bilirubin may resume treatment in the presence of Grade 2 AST/ALT OR total bilirubin.
- Subjects with combined Grade 2 AST/ALT AND total bilirubin values meeting discontinuation parameters should have treatment permanently discontinued
- Drug-related pulmonary toxicity, diarrhea, or colitis, must have resolved to baseline before treatment is resumed.
- Drug-related endocrinopathies adequately controlled with only physiologic hormone replacement may resume treatment.

If the criteria to resume treatment are met, the subject should restart treatment at the next scheduled time-point per protocol. However, if the treatment is delayed past the next scheduled time-point per protocol, the next scheduled time-point will be delayed until dosing resumes. For example, if a dose is missed for 5 weeks, a subject can re-start immediately but if dosing is delayed 3 weeks, a subject will need to wait until the next scheduled dose at 4 weeks.

Treatment may be delayed for up to a maximum of 8 weeks from the last dose; if treatment is delayed > 8 weeks, the subject must be permanently discontinued from study therapy, except as

specified in Section 5.6.7.5. Please see also Appendix 2 (Management Algorithms) for guidance on appropriate management and follow-up of adverse events.

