5.6.5.4 DOSE DISCONTINUATION OF NIVOLUMAB

Treatment should be permanently discontinued for the following:

- Any Grade 2 drug-related uveitis or eye pain or blurred vision that does not respond to topical therapy and does not improve to Grade 1 severity within the re-treatment period OR requires systemic treatment.
- Any Grade 3 non-skin, drug-related adverse event lasting > 7 days, with the following exceptions for drug-related laboratory abnormalities, uveitis, pneumonitis, bronchospasm, neurologic toxicity, hypersensitivity reactions, and infusion reactions:
 - Grade 3 drug-related uveitis, pneumonitis, bronchospasm, neurologic toxicity, hypersensitivity reaction, or infusion reaction of any duration requires discontinuation.
 - Grade 3 drug-related laboratory abnormalities do not require treatment discontinuation except:
 - Grade 3 drug-related thrombocytopenia > 7 days or associated with bleeding requires discontinuation
 - Any drug-related liver function test (LFT) abnormality that meets the following criteria require discontinuation:
 - AST or ALT > 8 x ULN
 - Total bilirubin > 5 x ULN
 - Concurrent AST or ALT > 3 x ULN and total bilirubin > 2 x ULN
- Any Grade 4 drug-related adverse event or laboratory abnormality, except for the following events which do not require discontinuation:
 - Isolated Grade 4 amylase or lipase abnormalities that are not associated with symptoms or clinical manifestations of pancreatitis and decrease to < Grade 4 within 1 week of onset.
 - Isolated Grade 4 electrolyte imbalances/abnormalities that are not associated with clinical sequelae and are corrected with supplementation/appropriate management within 72 hours of their onset.
- Any dosing delay lasting > 8 weeks with the following exceptions:
 - Dosing delays to allow for prolonged steroid tapers to manage drug-related adverse events are allowed. Prior to re-initiating treatment in a subject with a dosing delay lasting > 8 weeks, the PI must be consulted. Tumor assessments should continue as per protocol even if dosing is delayed.
 - Dosing delays > 8 weeks that occur for non-drug-related reasons may be allowed if approved by the PI. Prior to re-initiating treatment in a subject with a dosing delay lasting > 8 weeks, the PI must be consulted. Tumor assessments should continue as per protocol even if dosing is delayed.

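### For a hormone-controlled endocrinopathy at Grade 3 lasting more than 7 days, or at Grade 4, Section 5.6.5.3 permits resuming nivolumab while Section 5.6.5.4 calls for permanent discontinuation, and neither section says which governs

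*Combined protocol and SAP*

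**What the plan says.** Section 5.6.5.3 opens with a general condition for restarting: "Subjects may resume treatment with study drug when the drug-related AE(s) resolve to Grade ≤ 1 or baseline value, with the following exceptions". One of the exceptions that follow concerns endocrine toxicity: "Drug-related endocrinopathies adequately controlled with only physiologic hormone replacement may resume treatment". That line mentions no grade, no duration and no other section.

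Section 5.6.5.4 opens: "Treatment should be permanently discontinued for the following". Two entries matter here:

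- Grade 3: "Any Grade 3 non-skin, drug-related adverse event lasting > 7 days", with "exceptions for drug-related laboratory abnormalities, uveitis, pneumonitis, bronchospasm, neurologic toxicity, hypersensitivity reactions, and infusion reactions". For six of these event types the exception makes the rule stricter: "Grade 3 drug-related uveitis, pneumonitis, bronchospasm, neurologic toxicity, hypersensitivity reaction, or infusion reaction of any duration requires discontinuation". For laboratory abnormalities it makes the rule looser: at Grade 3 they do not require stopping, apart from listed thrombocytopenia and liver-test cases.
- Grade 4: "Any Grade 4 drug-related adverse event or laboratory abnormality, except for the following events which do not require discontinuation". The excepted events are isolated amylase or lipase abnormalities and isolated electrolyte abnormalities, each with conditions.

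Endocrinopathy appears in neither set of exceptions. Appendix 2 contains an endocrinopathy algorithm, but its grade-specific figure is not reproduced in the text available for this review.

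**The concern.** The line in 5.6.5.3 is a permission written for one class of event. The entries in 5.6.5.4 are general stopping rules that do not carve that class out. Where they overlap, an investigator who reads one section may give the next dose, and an investigator who reads the other ends treatment. Two institutions are planned to enrol, so like patients could be handled differently.

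Patient safety comes first, because the question is whether a patient is re-exposed after a severe immune-related event. Treatment exposure and the safety results are also involved. The synopsis builds the ability to complete six months of treatment into both safety endpoints, and the secondary hypotheses expect adverse events to be managed without interrupting nivolumab. Endocrinopathy is a foreseen toxicity: Section 5.6.5.1 names it among the managed groups, and the flow chart schedules thyroid tests.

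**Working it through.** The plan gives no figure to reproduce here. The check is a comparison of the two sections for a drug-related endocrinopathy controlled by physiologic hormone replacement alone.

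| Case | 5.6.5.3 | 5.6.5.4 | Result |
|---|---|---|---|
| Grade 2 | may resume | no grade-based entry applies | no conflict |
| Grade 3, 7 days or less | may resume | duration condition not met | no conflict |
| Grade 3, more than 7 days, recorded as a clinical event | may resume | discontinue | **conflict** |
| Grade 3, laboratory abnormality only | may resume | excepted | no conflict |
| Grade 4, any duration | may resume | discontinue | **conflict** |

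Three details fix the boundaries.

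1. Endocrinopathy is not among the six event types stopped at Grade 3 whatever their duration, so the 7-day condition applies to it.
2. The laboratory exception works at Grade 3 only, since the Grade 4 entry expressly covers laboratory abnormalities. Section 8.4 prefers clinical terms to laboratory terms where possible, which limits how often the exception would be used.
3. The plan does not say whether the 7 days count time spent at Grade 3 or the length of the whole event. Section 8.8 requires each change of grade to be recorded, so either count could be made. The first gives fewer Grade 3 conflicts. The Grade 4 conflict does not depend on it.

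Next, does the text say which section prevails? Other lines in 5.6.5.3 write in their limits. The Grade 2 skin line is closed to subjects who have had a Grade 3 drug-related skin event. The line on combined transaminase and bilirubin elevations refers to the discontinuation parameters. The endocrinopathy line does neither. The section's one numbered pointer to an exception from permanent discontinuation, in its 8-week delay rule, is to Section 5.6.7.5, which exists neither in the table of contents nor in the body.

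Scale for one patient:

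- Six doses are planned. If the event follows dose 2, the two readings differ by up to 6 − 2 = 4 doses.
- If all 39 patients are treated, one patient moves the completion proportion by 1/39 = 0.0256, or 2.6 percentage points.
- The plan expects 13% Grade 3 and 4 adverse events of all kinds: 0.13 × 39 = 5.07, about 5 patients. The affected endocrinopathies would be an unknown part of these, possibly none. This is a ceiling under the plan's own expectation, not an estimate.

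**The case against.** The strongest reply is that the rules are sequential. Section 5.6.5 says when to delay, 5.6.5.3 says when a delayed subject may restart, and 5.6.5.4 says who is out for good. A subject who has been permanently discontinued is no candidate to restart. On this view the endocrinopathy line relaxes only the requirement in its own lead-in, recovery to Grade 1 or baseline. It keeps a use for Grade 2 and short Grade 3 cases. The general restart rule has no ceiling on original grade either, so a missing ceiling alone would put much of 5.6.5.3 at odds with 5.6.5.4. The verbs also differ: one section permits and the other directs.

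This reading is coherent and may be what was meant. But no sentence states the order, and neighbouring lines spell out their limits where limits were wanted. The endocrinopathy line also differs from the general rule: it is an event-specific permission for toxicity that need not have resolved, and an investigator could reasonably take it as the more specific provision.

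The reply is right that the scope is narrow. Three stronger inferences are not supported:

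- A reader might infer that every Grade 3 endocrinopathy must be stopped. The Grade 3 entry applies only beyond 7 days, excepts laboratory abnormalities, and says should.
- A reader might infer that hormone-requiring endocrinopathies nearly always exceed 7 days, so almost all Grade 3 cases conflict. The documents give no durations, and the condition can persist after its grade has fallen.
- A reader might infer that Appendix 2 adds a further contradiction. Its figure cannot be read here, so it neither supports nor removes the conflict, and its absence from the text is not a fault in the plan.

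**Conclusion.** The point holds in a limited form. For a hormone-controlled drug-related endocrinopathy that is Grade 3 for more than 7 days and recorded as a clinical event, or Grade 4, the two sections read on their own terms give opposite instructions, and the protocol does not say which prevails. This rests on the visible text of 5.6.5.3 and 5.6.5.4 and on the absence of any stated order between them. The Appendix 2 figure might bear on it.

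The likely effect is small and cannot be quantified, since the documents give no expected number of such events. It falls on patient safety, doses received and the six-month completion part of the safety endpoints. A reader might infer that the primary analysis is affected. It is not affected through its population or the sample size: Section 9.1 includes everyone with at least one dose, and the power calculation uses none of these rules. The non-interruption hypotheses are only partly engaged, because Section 5.6.5 already delays dosing for most non-skin drug-related events from Grade 2 upward, before either rule is reached.

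**What to change.** Reconcile 5.6.5.3 and 5.6.5.4 so that both give the same instruction for hormone-controlled endocrinopathies that are Grade 3 for more than 7 days or Grade 4, and add a sentence saying which section governs when both apply. State whether the 7 days count time at Grade 3 or the length of the event. Correct the reference to Section 5.6.7.5. Check that the endocrinopathy algorithm in Appendix 2 is consistent with the result. Which rule applies is for the sponsor's clinicians to decide; this review takes no position.

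The cost is a few lines in a protocol amendment and a memo to the sites, with no added procedures or patients. If patients have already been treated, record which section was followed for any such case so that completion can be interpreted.
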